CABANA is a multi-center randomized clinical trial to assess the safety and efficacy of percutaneous left atrial catheter ablation versus antiarrhythmic drug therapy in subjects who are at least 18 years of age and have new onset or under-treated paroxysmal, persistent, or long-standing persistent atrial fibrillation (AF) and warrant therapy for their arrhythmia. The study population consists of 2,204 subjects enrolled at 126 clinical sites over a period of approximately six years. Subjects were randomized in equal proportions (1:1) to receive either catheter ablation or drug therapy and followed at regular intervals for the duration of the study. The minimum length of follow-up will be slightly less than 2 years, and the median duration of follow-up will be approximately 4 years. At study entry and during the follow-up period, extensive clinical, quality-of-life, and economic data are collected.

3. Objectives

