The treatment arms will be compared using statistical methods described in the sections above for other secondary endpoints, including the competing risk method of Fine and Gray⁴, as well as use of the log-rank test, hazard ratio and 95% confidence interval generated using the Cox model, and Kaplan-Meier cumulative event rate calculations. In this case, all-cause mortality will be a competing risk and zero-time (i.e., when the clock starts) for this analysis will be the end of the 90-day blanking period. Analyses will be repeated with adjustment for the baseline covariates described in section 8.1.

Of key interest will be whether the effect of ablation on recurrent atrial arrhythmias is similar or different according to the type of AF the patients experienced prior to enrolling in the trial (i.e., whether the effect varies according to whether patients’ baseline AF was paroxysmal, persistent or long-standing persistent). This analysis will utilize the Cox model to test for an interaction between the randomized treatment strategy and the baseline type of AF classified as (a) paroxysmal or (b) persistent or longstanding persistent. In addition to the interaction test, the effect of the treatment strategy characterized by a hazard ratio and 95% confidence interval and Kaplan-Meier event rate calculations will be calculated and displayed for the subgroups of patients whose baseline AF history was (a) paroxysmal and (b) persistent or longstanding persistent. Similar comparative analyses will be performed in subgroups defined by age (<65, 65-74, and ≥75) and by CHA₂DS₂-VASc Score (0 or 1 vs >1).

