9.9 Cardiovascular Hospitalization

A key part of the analysis and interpretation of the results of this endpoint will be the analysis performed in connection with secondary endpoint #2 (the composite of death or cardiovascular hospitalization). Analysis of cardiovascular hospitalization as an endpoint by itself must be analyzed and interpreted cautiously, particularly if there is a mortality difference between the two arms of the trial. If patients in one arm have lower mortality, that arm may have more hospitalizations simply because more patients are alive and at risk for needing to be hospitalized. Another important aspect of the analysis of this endpoint is that patients may have multiple hospitalizations, and so a comprehensive analysis of hospitalizations must take into account the recurrent hospitalization events rather than simply the first one. Consequently, there will be

several parts to the analysis of this endpoint in addition to a careful examination of the results of the composite endpoint consisting of death or cardiovascular hospitalization (see Section 9.2).

Statistical Methods:

- a. The first analysis will consider time until the first cardiovascular hospitalization in each arm and use the competing risks methodology of Fine and Gray⁵ where death from any cause is considered as a competing risk. The analysis will make use of the cumulative incidence function, and will be performed within the proportional hazards framework using the approach described in Section 9.4. The cumulative incidence function for each of the two arms will be estimated, statistically compared, and graphically presented using the PHREG procedure in SAS. For subjects who have not experienced a CV hospitalization, time from randomization until the subject's last follow-up contact will be used in the analysis. The level of significance for the assessment of this endpoint will be $\alpha=0.05$.
- b. An additional analysis of this endpoint will be performed using the log-rank test, hazard ratio and 95% confidence interval generated using the Cox model, and Kaplan-Meier cumulative event rate calculations. Patients who have died will be censored at the time of their death. This analysis and the approach in (a) above will be compared and summarized into an overall interpretation of treatment differences with respect to the endpoint of time to the first CV hospitalization.

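### SAP 9.8 plans only Kaplan-Meier event rates for the recurrent-AF subgroup displays; with death a competing event, these overstate the proportion of patients with recurrence

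*SAP*

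**What the plan says.** SAP 9.8 starts the clock at the end of the 90-day blanking period and compares the arms by Fine-Gray, log-rank, Cox and Kaplan-Meier methods. On death it states: "In this case, all-cause mortality will be a competing risk". It then turns to whether the ablation effect differs by baseline AF type. There it names a Cox interaction test and says that the "hazard ratio and 95% confidence interval and Kaplan-Meier event rate calculations will be calculated and displayed for the subgroups of patients", split into paroxysmal and persistent or long-standing persistent AF. It adds: "Similar comparative analyses will be performed in subgroups defined by age" (under 65, 65 to 74, 75 and over) and by CHA2DS2-VASc score. No cumulative incidence function is named for any of these subgroups.

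SAP 9.9 is organised differently. Item (a), the first analysis of time to first cardiovascular hospitalization, uses Fine-Gray with death competing: "The cumulative incidence function for each of the two arms will be estimated, statistically compared, and graphically presented using the PHREG procedure in SAS". Item (b) is an additional log-rank, Cox and Kaplan-Meier analysis that is open about its censoring: "Patients who have died will be censored at the time of their death". The SAP then says: "This analysis and the approach in (a) above will be compared and summarized into an overall interpretation of treatment differences". Sections 9.4 to 9.7 follow the same order, with cumulative incidence first and a disclosed death-censored analysis second.

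**The concern.** A patient who dies without recurrence can no longer have one. Kaplan-Meier with recurrence as the only event treats that patient as still able to recur later, like someone whose follow-up merely stopped. One minus Kaplan-Meier is then never below the actual cumulative proportion with recurrence, and it exceeds that proportion once deaths without recurrence are followed by further recurrences. SAP 9.8 accepts this reasoning for the overall comparison but does not carry it into the subgroup displays.

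At stake are the absolute percentages. Readers will take recurrence by AF type, and perhaps by age, from these displays as the chance that a patient recurs. For a given recurrence rate the excess rises with mortality, so percentages from subgroups with different death rates would not be on the same footing. Enrolling more patients would not remove this bias.

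**Working it through.** The documents state no event percentage for these displays, so there is no planned figure to reproduce. The check compares the two estimators under constant hazards, with λ the recurrence hazard and μ the death hazard:

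- one minus Kaplan-Meier, deaths censored: 1 − exp(−λt)
- cumulative incidence, death competing: λ/(λ+μ) × [1 − exp(−(λ+μ)t)]

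The time point is t = 4 years, because the SAP's opening description says that "the median duration of follow-up will be approximately 4 years".

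**Inputs**

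- Recurrence at 12 months in small randomized trials (Protocol 1.3.1): 24% after ablation, 76% on drugs. λ = −ln(0.76) = 0.274 and −ln(0.24) = 1.43 per year. Constancy after year 1 is assumed.
- A front-loaded alternative (Protocol 1.2.3, amiodarone): 33% at 1 year and 50% at 3 years. λ = −ln(0.67) = 0.400 in year 1, then ln(0.67/0.50)/2 = 0.146 per year, carried on to year 4.
- Projected drug-arm mortality (Protocol 8.1): 12% at 3 years. μ = −ln(0.88)/3 = 0.0426 per year.
- Low mortality: Protocol 8.1 says that aggregate mortality was below expectation but gives no figure. Half the projection is assumed: μ = −ln(0.94)/3 = 0.0206.
- High mortality (Protocol 1.1.2, population cohort with AF): 55% over 10 years at ages 55 to 75, μ = −ln(0.45)/10 = 0.080; nearly 70% at ages 75 to 94, read as 10 years by assumption, μ = −ln(0.30)/10 = 0.120.

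**Worked example: ablation recurrence rate, projected mortality**

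- One minus Kaplan-Meier: 1 − exp(−0.274 × 4) = 66.6%.
- Cumulative incidence: 0.274/0.317 × [1 − exp(−0.317 × 4)] = 62.2%.
- Excess: 4.4 points.

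**Cumulative incidence at 4 years, with the Kaplan-Meier excess in points in brackets**

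| Recurrence pattern | 1 − KM | Half projected mortality | Projected mortality | Ages 55–75 cohort | Ages 75–94 cohort |
|---|---|---|---|---|---|
| Ablation rate, constant | 66.6% | 64.4% (2.2) | 62.2% (4.4) | 58.7% (8.0) | 55.2% (11.5) |
| Drug rate, constant | 99.7% | 98.3% (1.4) | 96.8% (2.8) | 94.5% (5.2) | 92.0% (7.6) |
| Front-loaded | 56.8% | 55.4% (1.4 to 1.5) | 53.9% (2.9) | 51.5% (5.3) | 49.2% (7.6) |

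Across other constant recurrence hazards the excess at projected mortality peaks at 4.8 points, near 0.5 per year. That gives the range of roughly 1.4 to 5 points between half and full projected mortality. Very low recurrence gives less: at 0.05 per year it is 0.7 and 1.4 points for those two mortality rates. A simulation with staggered censoring (λ = 0.274, μ = 0.120) agreed with the formulas: 66.8% by Kaplan-Meier against 55.3% by the Aalen-Johansen estimate of cumulative incidence.

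**Between-arm gap at 4 years, constant drug and ablation rates, before rounding**

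- One minus Kaplan-Meier: 0.76⁴ − 0.24⁴ = 33.0 points.
- Cumulative incidence, projected mortality in both arms: 34.6 points.
- Cumulative incidence, projected drug-arm mortality and 8 to 9% at 3 years in the ablation arm (Protocol 8.1's projected ablation event rate, read as mortality): 33.1 to 33.5 points.
- Cumulative incidence, ages 75 to 94 death rate in both arms: 36.9 points.

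**The case against.** The strongest reply is that one minus Kaplan-Meier with deaths censored is the natural companion to a cause-specific Cox model, that the bias is small, and that the SAP handles competing death elsewhere. Much of this stands.

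- A reader might infer that 9.9 and 9.4 to 9.7 share the defect. They do not. Each puts the cumulative incidence first and discloses the censoring in the additional analysis. Section 9.9 compares the two approaches to interpret treatment differences; it does not merge percentages.
- A reader might infer that the overall 9.8 comparison lacks a cumulative incidence. It takes over the Fine-Gray method of the preceding sections, which includes one per arm.
- A reader might infer that the excess is greatest in patients aged 75 and over. This is plausible but not shown. The sentence on age does not itself mention Kaplan-Meier, and no trial recurrence or mortality by age is given. The ranking can also fail: 0.05 recurrences per year at the oldest cohort's death rate gives 3.6 points, less than the 4.4 points at the ablation rate with projected mortality. Section 9.9 plans no age subgroups at all.
- A reader might infer that treatment differences would be created or hidden. In the cases computed, the gap moves from 33.0 to between 33.1 and 36.9 points and never reverses.
- Size: in AF-type subgroups of an assumed 250 patients per arm, with lower assumed late recurrence, simulation gave an excess of 2.2 to 3.2 points, or 0.7 to 0.9 standard errors.

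What does not stand is that nothing needs changing. An unlabelled Kaplan-Meier percentage will be read as patient risk, and the subgroup displays are the one place in 9.8 with no cumulative incidence beside it.

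**Conclusion.** The point holds for the subgroup displays in SAP 9.8. Followed as written, they give percentages that exceed the proportion of patients with recurrence. The direction follows from the estimator. That deaths are censored there is implied by a Kaplan-Meier rate for recurrence alone; the SAP does not say so in words.

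The size is illustrative: roughly 1.4 to 5 points at 4 years for mortality between half and all of the projection, and about 7.6 to 11.5 points for the tabulated recurrence patterns at the ages 75 to 94 cohort death rate. It rests on outside recurrence and mortality figures quoted in the protocol, on independent and mostly constant hazards, and on applying those rates from the end of the blanking period. Since observed mortality was below projection, the lower part of the range may be nearer the truth overall.

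No hypothesis test, hazard ratio or primary-endpoint conclusion is affected.

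**What to change.** In the SAP 9.8 subgroup displays (AF type, age, CHA2DS2-VASc), replace the Kaplan-Meier event rates with the cumulative incidence function by arm, with all-cause death as a competing event. Keep the Cox hazard ratios, their confidence intervals and the interaction test, described as cause-specific.

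In 9.4 to 9.7 and 9.9(b) no replacement is needed. Label any Kaplan-Meier rate as censoring competing deaths, and state that the cumulative incidence is the reported patient risk.

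The cost is a few lines of SAP text and a change of output. The SAP already plans cumulative incidence for its arm comparisons. Data collection, sample size and significance levels are unchanged; the displayed recurrence percentages will be somewhat lower.

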9.9 Cardiovascular Hospitalization

A key part of the analysis and interpretation of the results of this endpoint will be the analysis performed in connection with secondary endpoint #2 (the composite of death or cardiovascular hospitalization). Analysis of cardiovascular hospitalization as an endpoint by itself must be analyzed and interpreted cautiously, particularly if there is a mortality difference between the two arms of the trial. If patients in one arm have lower mortality, that arm may have more hospitalizations simply because more patients are alive and at risk for needing to be hospitalized. Another important aspect of the analysis of this endpoint is that patients may have multiple hospitalizations, and so a comprehensive analysis of hospitalizations must take into account the recurrent hospitalization events rather than simply the first one. Consequently, there will be

several parts to the analysis of this endpoint in addition to a careful examination of the results of the composite endpoint consisting of death or cardiovascular hospitalization (see Section 9.2).

Statistical Methods:

- a. The first analysis will consider time until the first cardiovascular hospitalization in each arm and use the competing risks methodology of Fine and Gray⁵ where death from any cause is considered as a competing risk. The analysis will make use of the cumulative incidence function, and will be performed within the proportional hazards framework using the approach described in Section 9.4. The cumulative incidence function for each of the two arms will be estimated, statistically compared, and graphically presented using the PHREG procedure in SAS. For subjects who have not experienced a CV hospitalization, time from randomization until the subject's last follow-up contact will be used in the analysis. The level of significance for the assessment of this endpoint will be $\alpha=0.05$.
- b. An additional analysis of this endpoint will be performed using the log-rank test, hazard ratio and 95% confidence interval generated using the Cox model, and Kaplan-Meier cumulative event rate calculations. Patients who have died will be censored at the time of their death. This analysis and the approach in (a) above will be compared and summarized into an overall interpretation of treatment differences with respect to the endpoint of time to the first CV hospitalization.
- c. The analyses described above will be extended to a multiple events analysis, designed to take into account multiple hospitalization events that may occur during the course of a patient's follow-up. When considering one event per patient as in (a) or (b) above (i.e., the time until the first event), those events are independent because they occur in different patients. When considering multiple events for a patient, the events are no longer all independent because some of them are occurring within the same patient. This correlation (covariance) must be taken into account in deriving inferences. The multiple-event methods that will be used represent different extensions of Cox model methodology, and take into account the timing of the events and the correlation among multiple events occurring within an individual patient.

The main statistical approach will use a generalization of the Cox model developed by Andersen & Gill^{6,7}, with robust standard errors to account for heterogeneity and for the correlation between recurrent events within a patient.

Similar to time-to-1st event methods, a terminal event (death) could introduce bias in the recurrent events analysis, especially if there is a differential mortality between the study arms. Thus, the Ghosh and Lin⁸ nonparametric method can be utilized in calculating the cumulative rate of CV hospitalizations, while accounting for mortality as a competing risk. In addition, the average number of CV hospitalizations per 100-person years utilizing the Ghosh-Lin method can be calculated for each treatment group.

The Andersen-Gill recurrent events method will be performed using PROC PHREG in SAS software. However, the Ghosh-Lin method requires implementation of a validated package in R software.

9.10 Medical Costs, Resource Use and Cost Effectiveness.

Cost data will be analyzed by the CABANA EQOL Coordinating Center in close collaboration with the Data Coordinating Center, and the analysis approach will be detailed in a separate analytic plan.

9.11 Quality of Life.

Quality of life data will also be analyzed by the CABANA EQOL Coordinating Center in close collaboration with the Data Coordinating Center. Again, the analysis approach will be detailed in a separate analytic plan.

9.12 Major Non-Endpoint Adverse Events.

Major adverse events (AE) will be monitored and reported during the trial. For drug therapy, the major serious or life-threatening events include unanticipated hospitalizations for heart failure, drug-related pro-arrhythmic events, and pulmonary toxicity from amiodarone. For the ablation arm, the major events include symptomatic pulmonary vein stenosis requiring intervention, myocardial perforation/tamponade requiring intervention, and atrial-esophageal fistula formation. The frequency of each of these events (and other serious adverse events such as peripheral thromboembolic events) will be descriptively tabulated using MedDRA System Organ Class. Treatment comparisons with respect to these serious adverse events will be more descriptive rather than statistically rigorous (since different adverse events are expected in the two arms), bringing to bear clinical judgment as to the relative seriousness of these various adverse events. Other adverse complications or adverse events of either therapy will be tabulated and descriptively summarized, using statistical comparisons of the treatment groups based on chi-square tests where appropriate, and interpreting such comparisons in the context of treatment differences in the primary and major secondary clinical endpoints.

9.13 LA Size, Morphology and Function.

For the subjects participating in the CT/MR imaging sub-study, left atrial size, morphology, and function will be examined. Of interest will be the change in atrial size (volume) and function (i.e., atrial ejection fraction) from the pre-treatment to the post-treatment study within each treatment arm, and then importantly, a comparison of whether the change in size and function in the patients randomized to ablation therapy differs from the change in size and function of the patients randomized to drug therapy.

The distribution of these measures from the pre- and post-treatment studies in each treatment arm will be descriptively characterized using summary descriptive statistics and graphical tools including box and whisker plots. The statistical significance of the changes in left atrial volume and atrial ejection fraction from pre- to post-treatment studies within each treatment arm will be assessed using general linear models (GLM), including the baseline value as a covariate, and assessing treatment group differences. If there appears to be differences in other baseline

covariates between groups, adjustment for covariates will be considered. Secondary analyses will use a paired-sample t-test instead of GLM.

In dealing with this type of data, the completeness of which is dependent on obtaining both the pre- and post-treatment studies, there will inherently be missing data resulting from patients in whom it was not possible to obtain both studies (because they died or failed to return for other reasons to enable the follow-up measurements to be made). The completeness of the data will be fully described, and the statistical comparisons will be based on patients for whom both the baseline and follow-up studies are available.

10. “On-Treatment” Analysis

The intention-to-treat analyses in this trial will constitute the primary analyses and will serve as the standard for interpreting treatment differences in the key clinical outcomes. However, because a number of patients in the drug arm may cross over to receive ablation during the trial, and some patients randomized to ablation may not undergo the procedure, we will supplement the intent-to-treat comparisons of the primary endpoint and selected secondary endpoints with “on-treatment” comparisons. The “on-treatment” analysis will involve a comparison of patients who received ablation (even if originally assigned to the drug arm) versus those who did not. Statistically, this will be accomplished using the Cox proportional hazards model with ablation included in the analysis as a time-dependent covariate. This analysis will be repeated for the primary endpoint, all-cause mortality, all-cause mortality or cardiovascular hospitalization, all-cause mortality, stroke, or hospitalization for heart failure or acute ischemic events, cardiovascular death, cardiovascular death or disabling stroke, arrhythmic death or cardiac arrest, heart failure death, and cardiovascular hospitalization with and without adjustment for covariates listed in section 8.1. No analyses will include competing risks, and on-treatment analysis will not be conducted for multiple events analyses (section 9.9). For recurrent atrial fibrillation, we will only conduct this on-treatment analysis for the first episode of recurrent AF without competing risks in the 3 patient populations (Cabana box, non-cabana box, and pooled). Secondary analyses may consider other measures of recurrent atrial fibrillation (e.g., *symptomatic* recurrent AF, atrial fibrillation or atrial flutter or atrial tachycardia, and *symptomatic* atrial fibrillation, atrial flutter, or atrial tachycardia).

The time-dependent ablation variable to be included in the analysis will be created using 3 different methods: For method 1, the ablation variable starts as 0 (no ablation) for all patients. For patients who received ablation, the ablation variable is set to 1 at the time of ablation. In method 2, the ablation variable starts as 1 for all patients who were randomized to ablation and actually received ablation. For all other patients, the ablation variable is started as 0 and set to 1 at the time of ablation if they received ablation during the trial. Method 3 has the ablation variable started as 1 for patients who were randomized to ablation. For all other patients (i.e., randomized to drug), the ablation variable is started as 0 and set to 1 at time of ablation.

Among the 3 methods described above, method 2 will be considered the main statistical method in handling cross-overs via a time-dependent variable in Cox model. The other 2 methods are considered as sensitivity analyses.

Differential treatment effects for the primary endpoint and major secondary endpoints of interest using on-treatment analyses will also be conducted. Subgroups of interest will include those listed in section 8.1.

Because treatment assignment is no longer random, results can be biased by an association between the likelihood of treatment change and the risk of a clinical event (i.e., factors that make a patient more likely to cross over may also make them more likely to have an event). Thus, such analyses will be cautiously interpreted. Each of the analyses described in this section will be covariate adjusted using the covariates described in section 8.1 for the primary endpoint.

11. Per-Protocol Analysis

Using the methods described for the primary endpoint in Section 8, an analysis will also be performed to compare the primary endpoint and the key secondary clinical outcomes of the two treatment strategies among the subset of patients who fully satisfied the inclusion/exclusion criteria and received the treatment to which they were randomly allocated. This analysis will include patients randomized to the drug arm who were treated with drug therapy, and patients randomized to the ablation arm who underwent the ablation within 6 months following enrollment in the trial. The follow-up of drug-arm patients who crossed over to ablation will be censored at the time of the ablation. Patients randomized to the ablation arm who were not ablated within 6 months will be excluded from this analysis. Additional sensitivity analyses will be performed in which the window for ablation is varied to include a shorter interval (3 months) and a longer window (1 year).

The analyses outlined in Sections 10 and 11 will be strictly supplementary to the intent-to-treat analyses described earlier.

12. Multiple Comparisons

With the primary hypothesis and the various secondary endpoints that have been outlined, there is a multiplicity of analyses to be performed, which leads to an increased probability that at least one of the comparisons could be "significant" by chance. There are adjustments (e.g., based on the Bonferroni inequality) that could be used to preserve the overall type I error level. To attempt to adjust for the effects of the repeated significance testing that will occur as part of the interim monitoring (discussed below), plus adjust for the multiplicity of secondary endpoints, would require that very small significance levels be used for every comparison. The overall level of significance will be 0.049 for the assessment of the primary endpoint (see Section 13) and 0.05 for all secondary endpoints. However, to account in part for the multiplicity of comparisons involving secondary endpoints, we will be conservative in the interpretation of the analyses, taking into account the degree of significance, and looking for consistency across endpoints. The actual p-value for each comparison will be reported to aid in the overall interpretation. We have

also pre-specified the primary and secondary outcome variables to avoid over-interpretation of strictly exploratory comparisons.

13. Interim Analyses

For ethical reasons, an interim examination of key safety and endpoint data has been performed at regular intervals during the course of the trial. The primary objective of these analyses was to evaluate the accumulating data for an unacceptably high frequency of negative clinical outcomes in either of the treatment arms. In addition, the interim monitoring involved a review of the aggregated event rates, patient recruitment, compliance with the study protocol, status of data collection, and other factors which reflected the overall progress and integrity of the study. The results of the interim analyses and status reports were carefully and confidentially reviewed by an NHLBI-appointed Data and Safety Monitoring Board (DSMB).

The DSMB met at approximately 6-month intervals to review the accumulating data. Prior to each meeting, the Statistical and Data Coordinating Center (SDCC) at the DCRI conducted the desired statistical analyses and prepared a summary report for review by the DSMB. The extracted data files and analysis programs for each DSMB report were archived and maintained at the DCRI. Reports were presented describing the progress of patient enrollment, the rates of compliance with therapy, and the frequency of protocol violations. The SDCC also reported on the number (status) of data forms completed and the overall quality and completeness of the information.

In CABANA, a group sequential method similar to that proposed by O'Brien and Fleming⁹ was used as a guide in interpreting interim analyses. This procedure required large critical values early in the study, but relaxed (i.e., decreased) the critical value as the trial progressed. Because of the conservatism early in the trial, the critical value at the final analysis is near the "nominal" critical value. The actual method used for the interim monitoring was the Lan and DeMets¹⁰ group sequential method with monitoring boundaries based on a two-sided, symmetric O'Brien-Fleming type spending function. The Lan-DeMets approach only required specification of the rate at which the Type I error (which in this trial is $\alpha = 0.05$ for the primary endpoint) was "spent". The procedure allowed "spending" a portion of α at each interim analysis in such a way that at the end of the study, the total Type I error did not exceed 0.05. The specific formulation of the spending function is described in Chapter 5 of Proschan et al (formula 5.4)¹¹. Since the number of looks and the increments between looks did not need to be predetermined, it allowed considerable flexibility in the monitoring process for accommodating comparative examinations of the data in response to concerns of the DSMB that may arise during the course of the trial.

The analytic approach used at the interim analyses for assessing treatment differences consisted of the time-to-event analysis methods described previously, except that interpretation of statistical significance associated with treatment comparisons of key study endpoints was guided using the group sequential monitoring boundaries. The critical value of the test statistic and the

corresponding p-value required for significance was presented so that significance could be assessed precisely.

Although the CABANA DSMB has met approximately twice each year, the board has seen interim treatment-specific primary endpoint data only one time during the course of the trial. At all other meetings, only overall (aggregated) event data have been presented to them. As a result of the single treatment-specific DSMB presentation, the overall level of significance for the final analysis of the primary endpoint has been calculated to be .049 (using the O'Brien-Fleming boundary).

References

